2.2 BACKGROUND

MDD has been associated with hypoactivity in the left dorsolateral prefrontal cortex [3], characterized by elevated alpha oscillations [4]. Therefore, targeting and reducing alpha oscillations in the left dorsolateral prefrontal cortex could prove beneficial to patients with MDD. Targeted stimulation modalities, such as transcranial alternating current stimulation (tACS), can directly engage and modulate oscillatory activity. TACS utilizes sine-wave stimulation waveforms that can enhance specific oscillatory activity [5]. The proposed study is a follow-up to a recently concluded trial run by the Carolina Center for Neurostimulation under the direction of [name] [6].

This recently published trial compared the efficacy of 10Hz-tACS (therapeutic frequency, n = 10), 40Hz-tACS (control frequency, n = 10), and sham/placebo stimulation (n = 10). The intervention consisted of 5 consecutive days of 40-minutes of stimulation. Results demonstrated that 2-weeks after completion of the intervention, the 10Hz-tACS group had more subjects responding to treatment (i.e., at least a 50% decrease in depressive symptoms) as measured by the clinician-administered assessments (Montgomery-Asberg Depression Rating Scale, p = 0.026, and Hamilton Depression Rating Scale, p = 0.026). Concurrently, we found that 10Hz-tACS successfully reduced alpha oscillations in the left frontal regions after completion of the stimulation protocol (p < 0.05). While these data demonstrate preliminary efficacy, it is unclear how tACS caused this change, indicating a need to elucidate neurophysiological mechanism of action. Previous work from other groups demonstrate an increase in alpha oscillations following tACS (e.g., [[7]–[9]]), whereas our stimulation paradigm resulted in a decrease in alpha oscillations. Importantly, what is missing is the temporal course of these physiological changes and how they correspond to clinical outcomes. By including high-definition EEG before and after each stimulation, we will be able to delineate the neurophysiological reorganization of alpha oscillations in response to repeated application of tACS.

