3. OBJECTIVE AND OUTCOME MEASURES

OBJECTIVES	ENDPOINTS	JUSTIFICATION FOR ENDPOINTS
Primary		
To determine the effect of 10 Hz tACS on brain physiology as measured with electroencephalogram (EEG).	Resting state EEG recordings taken before/after every stimulation session, as well as at a 2-week follow up visit.	The focus is to determine the mechanism of action for five consecutive days of forty-minute tACS stimulation sessions. These endpoints will allow the examination of both immediate and long-term effects of 10 Hz tACS on physiology.
Secondary		
To elucidate the relationship between change in physiology and change in clinical symptoms	Correlations between Hamilton Depression Rating Scale (HDRS), Beck Depression Inventory (BDI) and alpha oscillation power (as measured by resting state EEG recordings).	Previous work indicates that 10 Hz tACS modulates mood and physiology, but there is no clear indication that these changes are related.

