9. STATISTICAL CONSIDERATIONS

9.1 STATISTICAL HYPOTHESES

- Primary Efficacy hypothesis:
 - Null: There is no difference in changes of alpha frequency power between baseline RSEEG and RSEEG at completion of stimulation between treatment regimens.
 - Alternate: There is a difference in changes of alpha frequency power between baseline RSEEG and RSEEG at completion of stimulation between treatment regimens.
- Secondary Efficacy hypothesis:
 - Null: There is no relationship between the changes in alpha frequency power and changes in Hamilton Depression Rating Scale, 17 item (HDRS17) scores.
 - Alternate: There is a relationship between the changes in alpha frequency power and changes in Hamilton Depression Rating Scale, 17 item (HDRS17) scores.

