9.2 SAMPLE SIZE DETERMINATION

In our recently concluded pilot clinical trial we compared the effects of 10 Hz tACS (therapeutic frequency) against 40 Hz tACS (control frequency) and sham/placebo stimulation. A total of 32 subjects enrolled, 30 completed the 5-day intervention, and 26 completed both a 2 and a 4-week follow-up session. With approximately 9 subjects in each group, a significant reduction was found in alpha oscillation power on the fifth day of stimulation ($p < 0.05$) [6]. Therefore, with a total of 20 subjects (10 in each group), we anticipate we will find a significant difference. Of note, our funding mechanism covers the cost of enrolling 20 participants.

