9.3 POPULATIONS FOR ANALYSES

Every effort will be made to ensure all enrolled and randomized subjects complete all study sessions as described in this protocol. However, *a priori*, we determined that our population for analysis will be a modified intention-to-treat (ITT) analysis dataset. For this study, enrolled eligible subjects will be randomized to receive 5 consecutive days of stimulation. If a subject completes the intervention (i.e., receives all 5 consecutive days of stimulation), they will be included in all analyses moving forward.

As previously stated in **Section 7 Study Intervention Discontinuation and Subject Discontinuation/Withdrawal**, enrolled subjects who do not complete the full intervention will be replaced. Therefore, with this population for analysis plan, we anticipate having data from 20 subjects that are eligible for analysis.

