9.4 STATISTICAL ANALYSES

9.4.1 GENERAL APPROACH

All testing described below assumes a significance threshold of $p = 0.05$. Continuous data will be described using means and standard deviations, while categorical data will be described using counts/percentages.

There will be no pre-specified covariates described in this protocol. Data will be assessed for normality and, if deemed necessary, corrective procedures will be applied (e.g., log normalization).

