9.4.2 ANALYSIS OF THE PRIMARY EFFICACY ENDPOINT(S) (EEG)

We will perform spectral analysis of resting state EEG from day 1 of stimulation (baseline), day 5 of stimulation, and the 2-week follow-up visit. We will use a repeated measure ANOVA and/or a general linear mixed-effects model (GLMM) to assess if there is statistically significant interaction between treatment (sham/placebo and 10 Hz tACS) and session (baseline, day 5 of stimulation, 2-week follow-up). In the case of missing data (e.g., missing follow-up visits), analysis using a GLMM will be prioritized, as GLMM takes into account missing data. Spectral analysis will be performed with multi-tapered estimation of the frequency spectrum followed by integration over the classical alpha EEG band (8-12 Hz).

In a separate analysis, we will perform spectral analysis of resting state EEG before and after each separate stimulation session. These analyses will be completed on the modified intention-to-treat dataset. Results from this section will be described in mean decibel (dB) change and presented using spectral images for visualization.

9.4.3 ANALYSIS OF THE SECONDARY ENDPOINT(S)(CORRELATION BETWEEN EEG CHANGES AND SYMPTOMS OF DEPRESSION)

Using the EEG results described in 9.4.2, mean dB change from baseline will be correlated with normalized change in HDRS17 scores.* Correlations will be assessed using Pearson's r and data will be plotted against the best fit line to visualize the results.

*HDRS17 normalization:

$[[\text{HDRS17 score at Visit \#}] - [\text{HDRS17 score at baseline}]] / [\text{HDRS17 score at baseline}]$

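### The secondary EEG–HDRS17 correlation has no term for arm, so on its own it cannot show a link beyond a shared effect of tACS

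*Combined protocol and SAP*

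**What the plan says.** Section 9.4.3 sets out the secondary analysis: "mean dB change from baseline will be correlated with normalized change in HDRS17 scores". The method is a simple correlation with a plot: "Correlations will be assessed using Pearson's r and data will be plotted against the best fit line to visualize the results". HDRS17 change is expressed as a proportion of the baseline score, visit by visit.

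Section 9.4.1 adds: "There will be no pre-specified covariates described in this protocol". Section 9.3 says of everyone who completes the five sessions that "they will be included in all analyses moving forward", and expects 20 analysable subjects; section 9.2 gives 10 per group.

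Treatment appears in the primary EEG model (9.4.2) and in the between-group safety comparisons (9.4.4), but not in 9.4.3. No partial correlation, within-arm correlation or mediation step appears anywhere.

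The secondary null in 9.1 does not mention arm: "There is no relationship between the changes in alpha frequency power and changes in Hamilton Depression Rating Scale, 17 item (HDRS17) scores". Section 3 justifies the endpoint this way: "Previous work indicates that 10 Hz tACS modulates mood and physiology, but there is no clear indication that these changes are related".

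**The concern.** Section 3 starts from the premise that stimulation moves both mood and physiology. Under that premise, a correlation taken across a stimulated and a sham group mixes two things: the association among participants who had the same treatment, and the difference between the arm means. If stimulated participants have on average both lower alpha power and lower HDRS17 scores, the two groups form two clouds displaced along a diagonal. Pearson's r across them is then positive even if neither cloud has any slope.

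The trial exists to study mechanism. A significant r could mean that tACS does two separate things, or that the two changes go together in individuals. The planned analysis has no step that tells these apart. The omission can also work the other way: if stimulation moves the measures in directions opposed to the within-arm association, the pooled r can hide a real link.

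**Working it through.** **Inputs from the documents.** 20 subjects, 10 per arm (9.2); Pearson's r without an arm term (9.4.3); significance threshold 0.05 (9.4.1), taken as two-sided because the alternatives in 9.1 are non-directional.

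**Inputs that are assumed.** The documents give no mean, SD, standardised effect or expected correlation, and no power figure for this analysis, so there is no planned figure to reproduce. I assume bivariate normal changes. The arms differ by d1 within-arm SD on alpha change and d2 on HDRS17 change at the same visit, and rw is the within-arm correlation.

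**Population value of the pooled r.** With 1:1 allocation the arm difference adds d1·d2/4 to the covariance and d²/4 to each variance, so

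r = (d1·d2/4 + rw) / √[(1 + d1²/4)(1 + d2²/4)].

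For example, d1 = d2 = 1.0 and rw = 0 gives 0.25/1.25 = 0.20. At 1.4 on both it is 0.49/1.49 = 0.33.

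**Tests compared.** Pooled r on 18 df has critical value 0.444. The partial correlation given arm, on 17 df, has critical value 0.456. Each setting was simulated with 200,000 trials; repeat runs agree to within about 0.3 percentage points.

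No within-arm relationship (rw = 0):

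| d1, d2 | Pooled r | Pooled test significant | Arm-adjusted test significant |
|---|---|---|---|
| 0.5, 0.5 | 0.06 | 5.7% | about 5% |
| 1.0, 0.5 | 0.11 | 7.5% | about 5% |
| 0.8, 0.8 | 0.14 | 8.9% | about 5% |
| 1.0, 1.0 | 0.20 | 13.7% | about 5% |
| 1.4, 1.4 | 0.33 | 31.7% | about 5% |
| 1.0, 0 | 0 | 5.0% | about 5% |

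The excess therefore needs an effect on both measures at the same visit.

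Within-arm correlation rw = 0.5:

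| d1, d2 | Pooled r | Power, pooled | Power, arm-adjusted |
|---|---|---|---|
| 0, 0 | 0.50 | 64% | 62% |
| 1.0, 0.5 (HDRS17 effect wholly through alpha) | 0.54 | 73% | 62% |
| 1.0, 1.0 | 0.60 | 85% | 62% |
| 1.0, 0 | 0.45 | 52% | 62% |
| 1.0, −1.0 | 0.20 | 10% | 62% |

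The last row is the case in which a real within-arm link is masked.

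**What the earlier trial says about d1 and d2.** For alpha, section 9.2 reports that "a significant reduction was found in alpha oscillation power on the fifth day of stimulation". For symptoms, section 2.2 reports that "2-weeks after completion of the intervention, the 10Hz-tACS group had more subjects responding to treatment". These are different visits and neither comes with an effect size, so the table cannot be narrowed to one row.

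**The case against.** The strongest reply is that the pooled r tests exactly what 9.1 writes down: no relationship between the two changes, without reference to arm. With a shift of 1.0 SD on both measures the population r is 0.20, so that null is false and the 13.7% are correct rejections of it. This stands. The pooled test is valid for marginal association; the criticism is that marginal association does not answer the question in section 3.

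Second, pooling is an inference. Section 9.3 fixes who is analysed, not whether r is computed across or within arms. The no-covariates sentence in 9.4.1 coexists with a treatment term in 9.4.2, so it does not plainly exclude arm here. This also stands, as a reason for the plan to say which it means. Pooling remains the more natural reading of a single Pearson r with one best-fit line on 20 subjects.

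Third, adjustment is not neutral. If tACS improves mood through alpha, the between-arm association is signal and adjustment discards it (73% against 62% power above). With a within-arm r of 0.3 the adjusted test has only about 24% power, so a non-significant result would say little, and a significant one would not prove mediation. All true. It argues for reporting both estimates, not for leaving the adjusted one out.

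Finally, this is a secondary analysis in a 20-person pilot and the size of the problem here is not known. That limits the weight of the point but does not remove it.

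**Conclusion.** The concern holds. As written, 9.4.3 yields one correlation that cannot by itself distinguish a shared effect of stimulation from a link between alpha change and symptom change. The consequence runs from negligible (5.7% significant at 0.5 SD on both measures) to substantial (31.7% at 1.4 SD on both), and is nil if tACS shifts only one measure at that visit.

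These figures assume 10 per arm, normal data, no within-arm correlation, pooled arms and a two-sided test. Which row applies to this trial is unknown. The change is worth making because the trial's stated purpose is mechanism and the remedy is cheap; nothing here invalidates the pooled r as a description of overall association.

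**What to change.** In 9.4.3:

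- State that Pearson's r is computed across both arms at each visit.
- Pre-specify beside it the partial correlation given arm, or equivalently a regression of normalised HDRS17 change on alpha dB change plus arm.
- Report both estimates with confidence intervals, and mark arm on the scatter plot.
- Rest any conclusion of an EEG–symptom link beyond the shared treatment effect on the arm-adjusted estimate.

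Align the covariate sentence in 9.4.1 with this. Do it before unblinding, so that the choice between the two readings is not made from the data.

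The cost is one model term and one degree of freedom, with no new data. By Fisher's z, the correlation detectable with 80% power is tanh[(1.96 + 0.84)/√17] = 0.59 pooled and tanh[(1.96 + 0.84)/√16] = 0.60 adjusted. Separate correlations within each arm of 10 would need tanh[(1.96 + 0.84)/√7] = 0.79, so one adjusted estimate is the better choice. The real cost is the loss of the between-arm information when the symptom effect runs through alpha. Keeping the pooled r in the report preserves it.

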9.4.4 SAFETY ANALYSES

As discussed in **Section 8.2, Safety and Other Assessments** safety will be assessed with the three questions from the daily suicide questionnaire, the C-SSRS, an adverse effects questionnaire, and the Young Mania Rating Scale (YMRS).

The suicide questionnaire is used as a screening to assess increase in suicidal ideation (SI) or suicidal behavior (SB) daily. The C-SSRS will be used to assess suicide risk more thoroughly. If a participant's responses on either tool indicate SI or SB, the subject will be contacted, and an acute assessment will be completed if deemed necessary by [name] or [name] (as described above). Any verified increases in suicidal ideation will be described in counts/percentages and compared between groups using chi-square tests.

The stimulation questionnaire will be administered following every stimulation session, for a total of 5 administrations per participant. This questionnaire solicits ratings of 14 possible adverse effects associated with electrical stimulation, on a scale of 1 (absent) to 4 (severe). Paired t-tests with random effect "subject" will be calculated per adverse effect to determine if there are any differences in adverse effect severity between groups (sham/placebo, 10 Hz tACS). Severity per adverse effect will be described with mean and standard deviation.

The Young Mania Rating Scale (YMRS) will be used to assess any development of mania over the course of treatment. A YMRS score of greater than 12 indicates the possible development of a manic episode. Any subject who scores greater than 12 on the YMRS will be assessed by [name] or [name]. Any verified manic episode will be described in counts/percentages and compared between groups using a chi-square test.

The Adverse Events Structured Interview will be administered by research personnel following every stimulation session and at the follow up visit, for a total of 6 time points per participant. This interview solicits open-ended descriptions of 11 possible adverse effects a participant may experience in any clinical trial as well as one question of 'any other experiences'. Responses will be reviewed by the clinician and rated as described in **Section 8.3**. Paired t-tests will be calculated per adverse effect to determine if there are any differences in adverse effect severity between groups (sham/placebo, 10 Hz tACS). Severity per adverse effect will be described with mean and standard deviation.3.

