We will be using the Suicide Item included in the HDRS-17 [12] to assess suicide risk, as well as the Columbia Suicide Severity Rating Scale (C-SSRS) [13] to determine intent for suicide during the screening interview. Inclusion criteria state that the subject must be low suicide risk and that potential subjects with an above “low risk” designation will not be eligible for the study. After the subject enrolls in the study, we will evaluate suicidal thoughts daily through an online questionnaire administered through REDCap. Additionally, the C-SSRS will be administered at D1, D5, and at the 2-week follow-up visit. In the event that suicide risk increases during participation in the study, the subject will be asked to stop the study. The subject will be provided with a referral to UNC Department of Psychiatry, and their mental health care or family medical doctor will be contacted.

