7. STUDY INTERVENTION DISCONTINUATION AND PARTICIPANT DISCONTINUATION/WITHDRAWAL

7.1 DISCONTINUATION OF STUDY INTERVENTION

Discontinuation from the week of stimulation does not mean discontinuation from the study, and remaining study procedures should be completed as indicated by the study protocol. If a clinically significant finding is identified (including, but not limited to changes from baseline) after enrollment, the investigator or qualified designee will determine if any change in subject management is needed.

The study intervention (i.e., the 5 consecutive days of stimulation) will be discontinued for the following reasons:

- A subject develops significantly increased suicidal risk, as determined by an acute assessment by [name] or [name].
- A subject has a YMRS score greater than or equal to 12.

- The subject misses a single day of stimulation and is unable to make it up at the end of the stimulation week.
- The subject fails to complete the online suicidality questions within 72 hours of receiving the survey email and a personal phone contact does not explain the omission.
- Any clinical adverse event (AE), laboratory abnormality, intercurrent illness or other medical condition, or situation occurs such that continued participation in the study would not be in the best interest of the subject.
- The subject meets any exclusion criteria (either newly developed or not previously recognized).

If the subject withdraws from the intervention, the subject will be contacted and invited for the 2-week follow-up assessment including all respective questionnaires. This assessment is not intended as a clinical follow-up with the participants but serves research purpose only.

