8.2 SAFETY AND OTHER ASSESSMENTS

8.2.1 SUICIDAL IDEATIONS AND SUICIDAL BEHAVIOR

Only subjects with a HDRS-17 suicidality item score of <3 and low suicide risk based on the C-SSRS are enrolled in this study. Furthermore, suicidal thoughts and behaviors will be assessed using a brief daily suicide survey (IRB# 14-0600) consisting of three questions. Participants will be asked if they had any thoughts of hurting themselves in the last 24 hours (suicidal ideation, SI) and whether they have hurt themselves in the past 24 hours (suicidal behavior, SB). They will also be asked to rate the severity of their depression on a scale of 1 to 10. Participants receive a link to answer the daily suicide survey on RedCap. To maximize participant's safety the daily suicide survey is send during the follow-up period as well. Responses will be monitored by study personnel daily and the last survey will be administered at the day of follow-up visit. In addition, the C-SSRS [13] will be administered by trained research personnel at screening, D1, D5 and the follow-up session to thoroughly assess suicide risk.

If a participant report experiencing either SI or SB on either tool, research personnel will collect more information from the participant to deliver to either [name] or [name]. Clinical personnel will decide if an acute assessment is required. Acute assessment may include facilitating contact of the subject with their psychiatrist or primary care physician to establish a plan for safety, continued care, and follow-up. If the participant does not have an established provider, [name] or [name] will assist in establishing a care plan. If at any point during the assessment, the participant is deemed an imminent risk of harm to self or others, study personnel will enlist the aid of campus security to ensure that the participant is safely escorted to the Emergency Department for further care. [name] and/or Dr.

[name] will decide if participation should be stopped after the acute assessment. If the participant is hospitalized, their participation will end.

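### The suicidality table in 9.4.4 has no by-arm count of self-harm, and with no safety population named it can miss a participant stopped mid-week for suicidal risk

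*Combined protocol and SAP*

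**What the plan says.** **Outcome.** Section 8.2.1 describes a three-question daily survey. One question asks about thoughts of self-harm (SI); a separate one asks "whether they have hurt themselves in the past 24 hours (suicidal behavior, SB". Section 9.4.4 lists all three questions among the safety measures and explains that "The suicide questionnaire is used as a screening to assess increase in suicidal ideation (SI) or suicidal behavior (SB) daily". The suicidality result it then commits to is: "Any verified increases in suicidal ideation will be described in counts/percentages and compared between groups using chi-square tests". Verified manic episodes get a by-arm count of their own in the same section, and adverse-event interview items are compared by severity. Section 9.4.1 adds a default format: "categorical data will be described using counts/percentages".

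**Population.** Section 9.3 states that "we determined that our population for analysis will be a modified intention-to-treat (ITT) analysis dataset". Participants who complete all five stimulation days enter all analyses, those who do not complete are replaced, and the result is that "we anticipate having data from 20 subjects that are eligible for analysis". Section 9.4.4 names no other set.

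**Stopping.** Section 2.3.1 says: "In the event that suicide risk increases during participation in the study, the subject will be asked to stop the study". Section 7.1 lists among its reasons for ending stimulation: "A subject develops significantly increased suicidal risk, as determined by an acute assessment". Under 8.2.1 the clinicians decide, after that assessment, whether participation stops.

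**The concern.** Two gaps meet in the same table.

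First, the survey treats self-harm as a separate item from ideation, and either one triggers contact with the participant, but only an increase in ideation is promised a count by arm. Self-harm in someone whose ideation has not risen from baseline would have no row.

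Second, during the stimulation week the event being counted can also be what takes the participant out of the only defined analysis set. Someone stopped after session 2 or 3 for suicidal risk is not a five-session completer, and under 9.3 a replacement fills the place. An analyst who builds the table on the one defined set would show the replacement and not the participant whose risk rose.

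At stake is what the trial reports about suicidality by arm, in a population where the predecessor saw increases in one arm only (four sham participants, none on tACS; 2.3.1). With about 10 per arm, one omitted participant can turn some events into none.

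**Working it through.** **Step 1: does any text give self-harm a by-arm count?**
- 9.4.4 lists event outcomes one by one (ideation increases, manic episodes). Self-harm is not among them.
- 9.4.1 sets a format but names no variable and no split by arm.
- 8.3.4 requires every adverse event to be documented, which is not a by-arm summary. The interview in 9.4.4 is analysed as mean severity per effect.
- The suspension criterion in 10.1.2 is trial-wide and concerns a need for extra clinical care.

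None supplies the count.

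**Step 2: can a mid-week stop leave the table?**
- 7.1 and 2.3.1 allow stimulation to end for suicidal risk, so the participant has fewer than five sessions.
- Under 9.3 such a participant does not meet the completion rule and is replaced. (7.2 is narrower: it replaces partial recipients who also leave the study. The broader rule is in 9.3.)
- 9.4.4 names no set that brings the participant back.

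So the participant can be missing, but only for events before session 5 is completed. Later events occur in completers.

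**Step 3: size.** The plan gives no expected event rate, so there is no planned figure to reproduce. Inputs: 10 per arm (9.2); predecessor sham arm n = 10 (2.2) with 4 participants reporting increased suicidal thoughts (2.3.1); predecessor 32 enrolled and 30 completing the five days (9.2), so 32 − 30 = 2 non-completers over all three arms. Assumption: each replacement is event-free and enters the same arm.

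With e events in an arm and k of them stopped and replaced, completers show (e − k)/10 and all stimulated show e/(10 + k). Intervals are Clopper-Pearson 95%.

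| Case | Completers | All stimulated |
|---|---|---|
| e = 1, k = 1 | 0/10 = 0% (0% to 31%) | 1/11 = 9% (0.2% to 41%) |
| e = 4, k = 0 | 4/10 = 40% (12% to 74%) | 4/10 = 40% (12% to 74%) |
| e = 4, k = 1 | 3/10 = 30% (7% to 65%) | 4/11 = 36% (11% to 69%) |
| e = 4, k = 2 | 2/10 = 20% (3% to 56%) | 4/12 = 33% (10% to 65%) |

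The range stops at k = 2 because the predecessor had only two non-completers in total, with reasons and arms not given.

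**Step 4: the planned test.** Each row is set against 0/10 in the other arm (two-sided p).

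| Table | Chi-square, uncorrected | Fisher exact | Smallest expected count |
|---|---|---|---|
| 4/10 v 0/10 | 0.025 | 0.087 | 2.0 |
| 3/10 v 0/10 | 0.060 | 0.21 | 1.5 |
| 4/11 v 0/10 | 0.034 | 0.090 | 1.9 |
| 2/10 v 0/10 | 0.14 | 0.47 | 1.0 |
| 4/12 v 0/10 | 0.044 | 0.096 | 1.8 |

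The choice of set moves the uncorrected chi-square across 0.05 (0.060 against 0.034 for k = 1; 0.14 against 0.044 for k = 2), while Fisher stays above 0.05 throughout. Expected counts of 2 or less make the chi-square p-values unreliable.

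**The case against.** The strongest reply is that the population point is a reading and not a rule. Section 9.3 says completers go into all analyses; it does not say non-completers are kept out of safety summaries. Section 9.4.2 ties the modified ITT set to the EEG analyses and 9.4.4 does not repeat it. Section 7.1 says that ending stimulation is not leaving the study and invites the participant to the two-week follow-up. All of this stands, and it is why the point is a gap and not an exclusion. It does not close the gap: the data may exist, but no text places them in the table, and 9.3 expects 20 analysable participants.

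On self-harm, 9.4.4 does name all three survey questions as safety measures, and many acts would also register as increased ideation. That also stands. What remains is mainly self-harm without a rise in ideation.

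Four stronger readings are tempting and not supported:
- *Participants are left unprotected.* Sections 7.1, 8.2.1 and 10.1.6 act on individual reports.
- *Every increase in risk leads to removal.* Section 2.3.1 taken alone suggests so, but 8.2.1 leaves the decision to clinicians after assessment.
- *All four predecessor sham participants could have vanished (0/10 against 4/14).* Only two participants in that whole trial did not complete.
- *The between-arm test is non-significant whichever set is used.* That holds for Fisher in the cases shown, not for the uncorrected chi-square.

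**Conclusion.** The point holds as a reporting gap that should be closed before unblinding. Self-harm has no planned by-arm count, and a participant stopped mid-week for suicidal risk can be missing from the one suicidality count that is planned. The first part follows directly from the text. The second rests on silence about a safety set, so the claim is that the participant can be missing, not that they will be.

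The effect is nil if nobody is stopped mid-week. One stop changes 0/10 to 1/11, and at the predecessor's event count with two stops the arm reads 20% or 33% depending on the set. These figures assume event-free replacements in the same arm, although 6.3 gives no rule for a replacement's arm. They also borrow a predecessor whose event timing and stopping rules are not given here. No figure can be put on the self-harm part, because the documents give no self-harm rate. The primary EEG analysis is untouched.

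**What to change.** In 9.4.4, define the safety set as every participant who received any stimulation, including those later withdrawn or replaced. Report by arm, as number and percentage of participants:
- (a) an increase in suicidal ideation over baseline;
- (b) any self-harm (SB) report.

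Give exact (Clopper-Pearson) 95% intervals, and call the between-arm comparison descriptive, because the expected counts are too small for a chi-square test. A sub-row for C-SSRS intent and a column for verification status would help but are optional.

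The cost is a few lines of text and one small table from data already collected. The downside is that safety denominators may differ from the 20 completers in the EEG analysis, which a footnote can explain.
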